4.6.2 Prohibited Medications

Subjects are prohibited from receiving the following therapies during the Screening and Treatment Phase of this trial:

- Anti-cancer systemic chemotherapy or biological therapy ≤ 28 days prior to starting study treatment
- Immunotherapy not specified in this protocol ≤ 28 days prior to starting study treatment

NU Study Number: NU 16N03
BMS Study Number: CA 209-802

- Chemotherapy not specified in this protocol ≤ 28 days prior to starting study treatment
- Investigational agents other than nivolumab or ipilimumab ≤ 28 days prior to starting study treatment
- Radiation therapy
- NOTE: Palliative radiation on study is permitted. Refer to Section 4.6.1.1 for details.
- Live attenuated vaccines ≤ 30 days prior to starting study treatment
NOTE: Influenza vaccination should be given during influenza season only (approximately October to March). Patients must not receive live, attenuated influenza vaccine (e.g., FluMist) ≤ 30 days prior to study treatment or at any time during the study.
- Corticosteroids are not permitted ≤ 14 days prior to study treatment unless they fall under the criteria listed in 4.6.1

4.7 Duration of Therapy

In the absence of treatment delays due to adverse event(s), treatment may continue until one of the following criteria applies:

- Disease progression (please refer to 4.4 for guidance regarding treatment beyond progression),
- Intercurrent illness that prevents further administration of treatment,
- Unacceptable adverse event(s) as already described in session.
- Patient holds drug for ≥6 weeks (42 days) for reasons of toxicity (or 60 days with approval from the DSMC)

4.8 Duration of Follow Up

All patients will be followed for adverse events for 30 days after last dose of nivolumab and or ipilimumab (100 days for SAEs), or until the patient starts a new treatment, whichever occurs first. Patients who discontinue treatment for unacceptable adverse event(s) will be followed until resolution or stabilization of the adverse event (i.e. the grade is not changing). If a patient stops treatment due to unacceptable adverse event(s) but has not demonstrated disease progression, then the patient will be followed with imaging studies every 12 weeks until the time of progression radiographically according to RECIST 1.1 criteria. In the event that a radiographic response is detected, then this event will be included as a response in the final analysis, and the time of progression used in calculation of the survival analysis. Patients will be seen in clinic every 4 weeks for the first 12 weeks after treatment discontinuation. Thereafter, patients will be followed for survival (by clinic visit or phone call) every 12 weeks for 2 years from treatment discontinuation or until death, whichever occurs first.

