Safety data for subjects with previously untreated unresectable or metastatic melanoma treated with nivolumab in combination with ipilimumab in phase III (313 subjects) and phase II (94 subjects) trials were pooled and safety analyses were performed for these pooled subjects receiving nivolumab in combination with ipilimumab (a total of 407 subjects) as described in the investigator brochure BMS-936558/MDX1106 Version No14, 30-Jun-2015.^{22,38} Based on the pooled analyses, nivolumab 1 mg/kg combined with ipilimumab 3 mg/kg administered IV Q3W for 4 doses followed by nivolumab 3 mg/kg IV Q2W has an acceptable safety profile, as demonstrated by the frequency, severity, and types of AEs, drug-related deaths, SAEs, and AEs leading to discontinuation. The most frequently reported drug-related AEs of any grade were diarrhea (43.0%), fatigue (35.4%), pruritus (33.4%), rash (31.0%), nausea (24.8%), pyrexia (18.7%), ALT increased (18.2%), AST increased (16.7%) and decreased appetite (16.2%). The most frequently reported drug-related Grade 3-4 AEs ($\geq 5\%$ of subjects) were colitis (9.6%), diarrhea (8.80%), ALT increased (8.4%), lipase increased (8.4%), and AST increased (5.9%). Study drug toxicity was considered responsible for 2 deaths; 1 subject died of ventricular arrhythmia within 30 days of the last dose and the other died of pneumonitis between 31 and 100 days of the last dose.

Most recently, nivolumab at 3mg/Kg every 2 weeks combined with ipilimumab at 1mg/Kg every 6 weeks was administered in patients with advanced NSCLC in the first line setting (CheckMate 012 trial).²³ In this trial 4 different combinations of nivolumab were compared (nivolumab 1mg/Kg every 3 weeks x 4+ ipilimumab 1mg/Kg every 3 weeks x 4 followed nivolumab 3mg/Kg every 2 weeks (N=31), nivolumab 1mg/Kg every 2 weeks + ipilimumab 1mg/kg every 6 weeks (N=40), nivolumab 3mg/Kg every 2 weeks + ipilimumab 1mg/Kg every 12 weeks (n=38) and finally nivolumab 3mg/Kg every 2 weeks combined with ipilimumab 1mg/Kg every 6 weeks until disease progression (n=46). Toxicity data favored the latter group with estimates of grade 3 and 4 treatment related adverse events 29, 35, 29 and 28%, respectively. These results indicate that the nivolumab dose of 3mg/Kg administered every 2 weeks combined with ipilimumab 1mg/Kg every 6 weeks until disease progression has favorable disease profile and should be further explored in future clinical trials.

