2.2 Secondary Objectives & Endpoints

2.2.1 To assess the efficacy of nivolumab and ipilimumab according to response rate (RR), disease control rate (DCR; CR, PR, and SD at 6 and 12 months), overall survival (OS) and progression free survival (PFS) using RECIST criteria in patients with recurrent or metastatic ACC. ⁴⁴

The time in months from start of treatment to progression or death will be measured for all patients who receive at least one dose of study drug. Patients will be followed up to 2 years after completion of treatment. Efficacy will be evaluated in all patients who receive at least one cycle of study treatment.

2.2.2 To assess the efficacy of nivolumab and ipilimumab according to ORR, DCR, PFS, and OS in patients with recurrent or metastatic ACC using irRECIST criteria.⁴⁵ Efficacy will be evaluated in all patients who receive at least one dose of study treatment and have had their disease re-evaluated.

2.2.3 To assess the safety and tolerability profile of nivolumab and ipilimumab therapy in patients with recurrent or metastatic ACC using CTCAE version 4.03. The number, frequency, and severity of adverse events will be collected from time of consent until 30 days after study treatment for all patients who receive at least one dose of study drug.

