¹⁴ Archival tissue will be collected at baseline for all patients (if available). Additional tissue may be collected (if feasible) during biopsies performed as standard of care during study participation. Please see separate lab manual for details.

¹⁵ Treatment will start within 7 days after registration, and continue until confirmed disease progression, unacceptable toxicity, or withdrawal of consent. See section **4.4** for conditions to continue treatment beyond initial progression.

¹⁶ Study procedures may take place within 24 hours prior to study treatment.

¹⁷ End of Treatment visit will occur 30 days (\pm 7 days) after stopping nivolumab or combination treatment, or before the patient starts new treatment, whichever occurs first. Adverse events will be recorded for up to 30 days after stopping treatment (SAE's for 100 days).

¹⁸ Patients will be followed every 4 weeks (\pm 7 days) by routine clinic visit for the first 12 weeks after treatment. Thereafter, patients will be followed (either by routine clinic visit or by phone) every 3 months for up to 2 years to document survival and disease progression. SAE's will be recorded for the first 100 days after treatment discontinuation.

¹⁹ Echocardiogram and/or ECG should be performed at screening as clinically indicated for patients with a history of congestive heart failure or at risk because of underlying cardiovascular disease or exposure to cardiotoxic drugs. Cardiac toxicities should be closely monitored throughout treatment.

²⁰ Tissue will be collected for Next Generation Sequencing any time prior to study treatment (we will accept archival tissue from the lesion demonstrating progression of recurrent/metastatic disease, as long as the patient has not received other treatment since that biopsy). Tissue will also be collected with any SOC biopsies throughout study treatment. If a patient has not had NGS performed from the lesion demonstrating PD, and the lesion is amenable to biopsy, the patient may agree to provide a fresh biopsy for standard-of-care NGS. If a biopsy is not feasible, is a high-risk procedure for patient, or the patient is not willing, he or she will be required to provide blood for ct DNA and will not be excluded from the study.

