7.2.3 Serious Adverse Events (SAEs)

All SAEs, regardless of attribution, occurring from time of signed informed consent, through 100 days after the last administration of study drug, must be reported upon discovery or occurrence.

An SAE is defined in regulatory terminology as any untoward medical occurrence that:

- **Results in death.**
If death results from (progression of) the disease, the disease should be reported as event (SAE) itself.
- **Is life-threatening.**
The patient was at risk of death at the time of the event; it does not refer to an event that hypothetically might have caused death if it were more severe.
- **Requires *in-patient hospitalization or prolongation of existing hospitalization* for ≥ 24 hours.**
- **Results in *persistent or significant disability or incapacity*.**
- **Is a *congenital anomaly/birth defect*.**
- Is associated with an overdose.
For purposes of this trial, an overdose will be defined as any dose exceeding the prescribed dose for nivolumab or ipilimumab by 20% over the prescribed dose. No specific information is available on the treatment of overdose of nivolumab or ipilimumab. In the event of overdose, nivolumab should be discontinued and the subject should be observed closely for signs of toxicity. Appropriate supportive treatment should be provided if clinically indicated. If an adverse event(s) is associated with ("results from") the overdose of a BMS product, the adverse event(s) is reported as a serious adverse event, even if no other seriousness criteria are met.
If a dose of BMS's product meeting the protocol definition of overdose is taken without any associated clinical symptoms or abnormal laboratory results, the overdose is reported as a non-serious Event of Clinical Interest (ECI), using the terminology "accidental or intentional overdose without adverse effect."
All reports of overdose with and without an adverse event must be reported within 24 hours to the Sponsor and within 2 working days hours to BMS Global Safety.
- **Is an *important medical event*.**

Any event that does not meet the above criteria, but that in the judgment of the investigator jeopardizes the patient, may be considered for reporting as a serious adverse event. The event may require medical or surgical intervention to prevent one of the outcomes listed in the definition of "Serious Adverse Event".

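### Section 4.8 ends adverse-event and SAE follow-up when a new treatment starts; 7.2.3, 2.2.3 and footnotes 17-18 do not, and 6.3 adds a third AE window, so the passages need to be reconciled

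*Combined protocol and SAP*

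**What the plan says.** Section 4.8 (Duration of Follow Up) gives 30 days after the last dose for adverse events and 100 days for SAEs, and then continues: "or until the patient starts a new treatment, whichever occurs first". As the sentence is built, the new-treatment cut-off governs both windows. The same section follows patients who stop for toxicity until that event resolves or stabilises, and schedules clinic visits every 4 weeks for 12 weeks after treatment stops.

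The other collection rules have no such cut-off:

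- Section 7.2.3 requires all SAEs, irrespective of attribution, "through 100 days after the last administration of study drug, must be reported upon discovery or occurrence".
- Section 2.2.3, the safety objective, has adverse events "collected from time of consent until 30 days after study treatment for all patients who receive at least one dose of study drug".
- Footnote 18 of the Section 5.0 calendar: "SAE's will be recorded for the first 100 days after treatment discontinuation".
- Footnote 17 of the same calendar records AEs to 30 days and SAEs to 100 days. It brings the End of Treatment visit forward if new treatment is about to start, but leaves the recording windows alone.
- Section 6.3, the secondary endpoints, collects adverse events until 12 weeks after study treatment.
- Sections 8.1.11 and 8.2.11 follow all participants for side effects for 30 days from the last dose.
- Section 7.4.2 also requires reporting of events after day 30 if they are attributed to the study agents.

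**The concern.** Two sites can each follow the protocol and collect different safety data. Take a serious pneumonitis on day 60 in a patient who began another therapy on day 40. Section 7.2.3 requires it; under 4.8, follow-up for events ended 20 days earlier.

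Safety is a secondary objective, and Section 7.0 places the study under high-intensity monitoring. If 4.8 is followed, observation after the last dose is shortened only in patients who move to another therapy. Progression is a listed reason for stopping (4.7), and patients who stop for it are plausibly more likely to start something else. The length of safety observation could therefore be related to outcome.

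The protocol's background shows that late events occur with these drugs. Of two deaths attributed to study drug among 407 pooled melanoma patients (Section 1.2.4), one patient died of ventricular arrhythmia within 30 days and "the other died of pneumonitis between 31 and 100 days of the last dose".

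**Working it through.** No sample size, power or error rate is involved, so there is no planned figure to reproduce. The check compares the windows and then counts the days affected.

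**Windows side by side**

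| Place | AEs after treatment | SAEs after treatment | Ends at new treatment? |
|---|---|---|---|
| 4.8 | 30 days | 100 days | Yes, both |
| 7.2.3 | not addressed | 100 days | No |
| 2.2.3 | 30 days | not separate | No |
| Footnote 17 | 30 days | 100 days | No (visit only) |
| Footnote 18 | not addressed | 100 days | No |
| 6.3 | 12 weeks = 84 days | not separate | No |
| 8.1.11, 8.2.11 | 30 days | not separate | No |

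There are two conflicts: the cut-off appears only in 4.8, and the AE window is 30 days in some places and 84 in another.

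**Do other provisions close the gap?**

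- The toxicity exception in 4.8 follows the event that stopped treatment. It does not cover a new event in a patient who stopped for progression.
- Section 7.1 follows events that have already occurred. It does not say how long new ones are sought.
- Section 7.4.2 covers events after day 30 only if they are attributed to study drug. Section 7.2.3 covers SAEs irrespective of attribution, and attribution is hardest once another therapy has begun.

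The exposed case is therefore a serious event after new therapy starts, not attributed to study drug, in a patient who stopped for another reason such as progression. Only 7.2.3 and the footnotes call for it, and 4.8 says follow-up has ended.

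**Days affected in one patient who starts new therapy on day d, if 4.8 governs**

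Days lost = max(0, W − d), where W is the window. The values of d are assumptions; the documents give none.

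| d | SAE, W = 100 | AE, W = 30 | AE under 6.3, W = 84 |
|---|---|---|---|
| 14 | 86 | 16 | 70 |
| 28 | 72 | 2 | 56 |
| 42 | 58 | 0 | 42 |
| 60 | 40 | 0 | 24 |

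If 7.2.3, 2.2.3 and the footnotes govern, the loss is zero in every row. With the 30-day AE window the conflict is mainly about SAEs, since AEs are affected only when new therapy starts before day 30. If the 12-week window in 6.3 is the intended one, AEs are affected as well.

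**Visits.** Clinic visits every 4 weeks for 12 weeks end at 12 × 7 = day 84. The remaining 100 − 84 = 16 days (85-100) have no scheduled clinic visit.

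**The case against.** The strongest reply is that nothing need be lost. Section 7.2.3 makes SAEs to day 100 mandatory. Section 7.4.3 requires each SAE to be reported within 24 hours, with no exception for new therapy, and 7.4.2 adds attributed events after day 30. The 4-weekly clinic visits in 4.8 carry no new-treatment cut-off, so most patients are still seen. This stands as far as it goes. A reader might infer that late immune-related events are in fact dropped; the documents support only that they may be missed where a site takes 4.8 as its rule.

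Other stronger readings also fail:

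- **That the loss falls mainly on patients who progress.** This is plausible but not shown. No rate or timing of later therapy is given, 4.4 lets some patients stay on study drug after progression, and Section 1.1 says there is no standard systemic treatment for ACC.
- **That a share of follow-up lost can be quoted.** The share of days 31-100 lost is p × (100 − d)/70. Assuming p = 0.3 and d = 45 gives 0.3 × 55/70 = 24%; assuming p = 0.7 and d = 30 gives 70%. That spread reflects the chosen inputs and estimates nothing about this trial.
- **That the safety endpoint in 2.2.3 is biased.** Its window closes at day 30, so it is touched only if new therapy starts before then.
- **That denominators become unequal.** Section 6.8 makes every patient given nivolumab evaluable for toxicity, and 10.3 plans frequencies and percentages. The denominator is patients; only the length of observation could differ.
- **That the pneumonitis death shows the harm of the cut-off.** It is one event in 407 patients with a different disease and regimen, and nothing says that patient had begun new therapy. It supports a 100-day SAE window, which 4.8 already has.

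It is also arguable that stopping at new therapy keeps the next drug's toxicity out of the tables. That is a legitimate choice, but 7.2.3 has already chosen otherwise for SAEs.

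**Conclusion.** The point holds as an internal contradiction with a possible effect on SAE ascertainment. The new-treatment cut-off in 4.8 conflicts with 7.2.3, 2.2.3 and footnotes 17-18, and the AE window itself conflicts between 6.3 and the 30-day passages. Where 4.8 is followed, SAEs after new therapy may be missed, mainly in days 31-100, and observation length would vary with whether and when a patient starts another therapy.

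The size across the trial cannot be stated. The per-patient days in the table rest on assumed start days and on 4.8 overriding the other sections; a link to progression is a reasonable inference only. The primary PFS analysis is not affected. The plan should be corrected because the edit is small and the possible loss may be related to outcome.

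**What to change.** 1. In the event-collection sentence of 4.8, delete "or until the patient starts a new treatment, whichever occurs first", so that it agrees with 7.2.3 and footnotes 17-18. The timing of the End of Treatment visit in footnote 17 can stay.
2. Choose one AE window and use it in 2.2.3, 4.8, footnote 17 and 6.3, carrying it into 8.1.11 and 8.2.11.
3. Define new treatment and record its start date on the CRF for every patient. The concomitant-medication rule in 4.6.1 stops at 30 days after the last dose unless an SAE is involved, so it would not reliably capture a later start.
4. Flag events on or after that date, with investigator attribution, and present the AE tables with and without them.
5. Add a telephone call or record check at about day 100, because the 4-weekly visits end at day 84.

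The cost is a short text amendment, one CRF date, one flag and one added contact or record check per patient. The main downside is that some events caused by the next therapy will be collected and must be labelled, which is what the flag is for.

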4.9 Removal of Subjects from Study Treatment and/or Study as a Whole

Patients can be taken off the study treatment and/or study as a whole at any time at their own request, or they may be withdrawn at the discretion of the investigator for safety, behavioral or administrative reasons. The reason(s) for discontinuation must be clearly documented on the appropriate eCRF and may include:

- Patient voluntarily withdraws from treatment (follow-up permitted)
- Patient withdraws consent (no follow-up permitted)
- Patient is unable to comply with protocol requirements (follow-up permitted)
- Patient demonstrates disease progression (per parameters above, follow-up permitted)
- Patient experiences unacceptable toxicity
- Treating physician determines that continuation on the study would not be in the patient's best interest

NU Study Number: NU 16N03
BMS Study Number: CA 209-802

- Patient becomes pregnant
- Patient develops a second malignancy that requires treatment which would interfere with this study
- Patient becomes lost to follow-up (LTf)

4.10 Patient Replacement

Any patient who signs consent but does not receive study treatment may be replaced.

5.0 STUDY PROCEDURES

	Screening ¹	On Treatment ^{15,16} (1 cycle = 12 weeks / 84 days)														Off Treatment				
		Cycle 1 (Each visit -2/+4 days)							Cycle 2 (Each visit -2/+4 days)							Cycle 3+ (Each visit -2/+4 days)				
		Day of each cycle	1	15	29	43	57	71	1	15	29	43	57	71	1	15	29	43	57	71
	Weeks on study	1	3	5	7	9	11		13	15	17	19	21	23	25	27	29	31	33	35+
Informed Consent	X																			
Medical history	X																			
Physical exam ²	X	X		X					X		X			X		X			X	
ECOG status	X	X		X					X		X			X		X			X	
Adverse Events & ConMeds	X		X	X	X	X	X	X	X	X	X	X	X	X	X	X	X	X	X ¹⁷	
Scans (C/A/P/N) ^{3,4,5}	X ₃								X _{4,5}					X _{4,5}					X ₅	
CBC with diff ⁶	X	X	X	X	X	X	X	X	X	X	X	X	X	X	X	X	X	X	X	
Chemistry panel ⁷	X	X	X	X	X	X	X	X	X	X	X	X	X	X	X	X	X	X	X	
Amylase/Lipase ⁸	X	X		X					X		X			X		X			X	
TSH with reflex ⁹	X	X		X					X		X			X		X			X	
Echo/ECG ¹⁹	X ₁₉																			
Tissue for NGS ²⁰	X ₂₀	X ₂₀																		
Liquid biopsy ²¹	X ₂₁	X ₂₁							X ₂₁					X ₂₁					X ₂₁	
Pregnancy test ¹⁰	X	X																		
Nivolumab administration ¹¹	T	T	T	T	T	T	T	T	T	F	F	F	F	F	F	F	F			
Ipilimumab administration ¹²	X		X					X		X			X		X					
Study Labs ¹³	X											X ₁₃							X	
Tissue collection ¹⁴	X											X ₁₄								
Survival status																			X ₁₈	

T = 240mg nivolumab

F = 480mg nivolumab

¹ Screening procedures must take place within 28 days of registration unless otherwise specified (CBC with diff and Chemistry panel should be within 14 days of registration; scans should be within 28 days prior to starting treatment);

² Includes vital signs (pulse, blood pressure) and height (baseline only) and weight.

³ Imaging scans must include recurrent and/or metastatic disease, and must be within 28 days prior to starting study treatment. If a patient is scheduled to start treatment >28 days after the last scan, imaging must be repeated. Per treating investigator's discretion, images may include Neck, Chest, Abdomen, and Pelvis (or any combination to perform tumor assessment). Scans may be by CT, PET/CT or MRI (per treating investigator's

Initial Version: 11/23/2016

Amendment 8: 10/6/2022

discretion) with contrast unless strictly contraindicated; the same modality used at baseline should be used throughout. Brain MRI should be performed at baseline if clinically indicated, \leq 6 weeks prior to registration. Tumor assessment (incorporating both RECIST and clinical criteria) should be done Day 1 of every cycle, i.e. every 12 weeks (\pm 7 days) starting with Cycle 2, until progression or treatment discontinuation whichever occurs first.

⁴ Earlier scans may be performed at the discretion of the treating physician.

⁵ If PD is confirmed at any time, see section **4.4** on how to determine whether patient can be considered for further treatment. If patient continues, scans should be obtained every 8 weeks until PD is confirmed by 2 consecutive scans.

⁶ CBC with differential will be collected within 14 days of registration and at each treatment visit, pre-treatment. It will include WBC, ANC, ALC, Platelets, and Hemoglobin.

⁷ Chemistry panel will be collected within 14 days of registration and at each treatment visit, pre-treatment. It will include glucose, calcium, albumin, ALT, AST, sodium, potassium, total bilirubin, alk phos, and creatinine.

⁸ Amylase and lipase will be assessed at screening and every 6 weeks (Day 1 and 43 of each cycle) pre-treatment.

⁹ TSH will be tested at screening and every 6 weeks (Day 1 and 43 of each cycle), pre-treatment. If TSH is abnormal, free T4 should be tested

¹⁰ Serum or urine test for females of child-bearing potential (FOCBP) \leq 14 days prior to registration. FOCBP are also required to have a negative pregnancy test within 24 hours of starting nivolumab.

¹¹ Nivolumab will be administered in combination with ipilimumab as follows:

First 8 doses (Cycle 1, C2D1, & C2D15): 240mg IV q2weeks

Starting with C2D29: 480mg IV q4weeks until disease progression, intolerable toxicity or withdrawal of consent.

¹² Ipilimumab will be administered IV at 1mg/kg over 90 minutes every six weeks in combination with nivolumab. Dosing will be based on weight at baseline unless there is a change \geq 10%. Nivolumab will be given before ipilimumab.

¹³ A correlative blood sample (3x 8ML heparin tubes) will be drawn at baseline (C1D1, pre-dose), at the first scheduled study visit after response is confirmed (PR or CR), and at the end of treatment visit. Please see separate lab manual for details.

¹⁴ Archival tissue will be collected at baseline for all patients (if available). Additional tissue may be collected (if feasible) during biopsies performed as standard of care during study participation. Please see separate lab manual for details.

¹⁵ Treatment will start within 7 days after registration, and continue until confirmed disease progression, unacceptable toxicity, or withdrawal of consent. See section **4.4** for conditions to continue treatment beyond initial progression.

¹⁶ Study procedures may take place within 24 hours prior to study treatment.

¹⁷ End of Treatment visit will occur 30 days (\pm 7 days) after stopping nivolumab or combination treatment, or before the patient starts new treatment, whichever occurs first. Adverse events will be recorded for up to 30 days after stopping treatment (SAE's for 100 days).

¹⁸ Patients will be followed every 4 weeks (\pm 7 days) by routine clinic visit for the first 12 weeks after treatment. Thereafter, patients will be followed (either by routine clinic visit or by phone) every 3 months for up to 2 years to document survival and disease progression. SAE's will be recorded for the first 100 days after treatment discontinuation.

¹⁹ Echocardiogram and/or ECG should be performed at screening as clinically indicated for patients with a history of congestive heart failure or at risk because of underlying cardiovascular disease or exposure to cardiotoxic drugs. Cardiac toxicities should be closely monitored throughout treatment.

²⁰ Tissue will be collected for Next Generation Sequencing any time prior to study treatment (we will accept archival tissue from the lesion demonstrating progression of recurrent/metastatic disease, as long as the patient has not received other treatment since that biopsy). Tissue will also be collected with any SOC biopsies throughout study treatment. If a patient has not had NGS performed from the lesion demonstrating PD, and the lesion is amenable to biopsy, the patient may agree to provide a fresh biopsy for standard-of-care NGS. If a biopsy is not feasible, is a high-risk procedure for patient, or the patient is not willing, he or she will be required to provide blood for ct DNA and will not be excluded from the study.

²¹ A liquid biopsy (blood sample for ctDNA) will be collected at baseline (any time prior to study treatment). If a patient already had this test, we will accept that, as long as the patient has not received other treatment since that liquid biopsy was obtained. During the course of treatment, patients will be asked to have repeat ctDNA testing, as per standard of care procedures, progression of disease, and as clinically indicated.

